5.2.3 Subgroup Analyses

We will explore two clinically relevant subgroups based on life expectancy at baseline and fracture status. Life expectancy will be dichotomized as life expectancy of greater than or equal to one year versus less than one year, and fracture status will be classified as either impending fracture or realized pathologic fracture. We hypothesize that participants with a longer life expectancy and those with an impending fracture prior to surgery will have greater treatment benefits from the more invasive surgical procedure. We will stratify our primary model by the subgroup covariate to assess the presence of effect modification. We will assess the credibility of any observed subgroup effects using the Instrument to assess the Credibility of Effect Modification Analyses (ICEMAN) criteria.

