2.2 Subgroup Objectives

We will explore two clinically relevant subgroups based on life expectancy at baseline and fracture status. Life expectancy will be dichotomized as life expectancy greater than one year versus less than one year, and fracture status will be classified as either impending fracture or pathologic fracture. *We hypothesize that patients with a longer life expectancy and those with an impending fracture prior to surgery will have greater treatment benefits from the more invasive surgical procedure.*

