4.4 Randomization

After providing informed consent, participants will be randomized in a 1:1 ratio to receive either resection and reconstruction or internal fixation. A centralized web-based randomization system (www.randomize.net) will be used to ensure the concealed allocation of participants. Treatment allocation will be determined using random variable block sizes to avoid a substantial imbalance in the number of participants assigned to each treatment group. To ensure balance across groups for any key prognostic and treatment-related variables, such as regional differences in MBD management, the randomization process will be stratified by: 1) impending or pathologic fracture, and 2) clinical site.

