5.0 Statistical Plan

5.1 Sample Size Determination

The use of hierarchically assessed composite outcomes is becoming more frequent in clinical trials, and it offers several benefits. By utilizing a pre-defined rank, statistical power increases while avoiding concerns of increased type I errors due to multiplicity. This ranked approach also aligns with clinical practice as patients and care providers are typically interested in the treatment effect on multiple outcomes with a defined hierarchy. Detailed simulations were performed to determine the appropriate sample size to adequately power the study. **Table 5** lists the distributional assumptions for each component of the composite outcome by treatment arm. Using 10,000 simulations of these distributions, we determined that 300 patients (150 per group) provided over 90% power to detect superiority with a two-sided alpha of 5% tested with the U-statistic described by Bebu and Lachin²⁶. To account for up to 10% attrition, the trial plans to enroll 334 patients.

Table 5 : Input for sample size estimation.

Rank	Outcome	Resection and Reconstruction	Internal Fixation
1	Death within 12 months	30%	30%
2	Physical function (ability to perform everyday activities) by 4 months		
	Unable to do	5%	10%
	With much difficulty	20%	25%
	With some difficulty	40%	40%
	With little difficult	25%	20%
	Without any difficulty	10%	5%
3	Days at home within 365 days, mean (SD)	340 (20)	300 (20)

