5.2.2 Primary Outcome Analysis

We will hierarchically assess the primary composite outcome using the Win Ratio method. The Win Ratio method is based on the principle that each participant in the clinical trial is compared with every other participant within each stratum in a pairwise manner. All-cause mortality comparisons will be time-to-event and local cancer recurrence will allow for recurrent events using a frailty model. The pairwise comparison proceeds in a hierachal fashion – for example, starting with mortality, followed by physical function, followed by days at home, and finally by local cancer recurrence when participants cannot be differentiated on an outcome of higher importance. If two paired participants both experienced a local cancer recurrence, we will assume a greater frequency of recurrences to be worse. If two paired participants have the same mortality status or frequency of recurrences, we will assume earlier events are worse. For each pairwise comparison, the treatment groups are assigned a

win, loss, or tie. The Win Ratio is the frequency of a favorable outcome in participants assigned to resection and reconstruction divided by the frequency of a favorable outcome in participants assigned to internal fixation with a 95% CI and corresponding p-value calculated using the methods described by Finkelstein and Schoenfeld.

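### Effect modification by life expectancy is judged only on the win ratio, which moves towards 1 in whichever subgroup has more deaths, even if surgery works equally well in both

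*Protocol*

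**What the plan says.** Section 2.2 defines the first subgroup: "Life expectancy will be dichotomized as life expectancy greater than one year versus less than one year". Section 5.2.3 repeats it, with one year exactly placed in the longer group. Both sections predict more benefit from resection in patients expected to live longer and in those with an impending fracture.

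The method in section 5.2.3 is one sentence: "We will stratify our primary model by the subgroup covariate to assess the presence of effect modification". No other scale for effect modification is named. ICEMAN is cited for judging the credibility of any subgroup effect that is seen.

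The primary model (section 5.2.2) is a win ratio with pairwise comparison "starting with mortality, followed by physical function, followed by days at home". Mortality is compared as time to event and, between two patients with the same mortality status, the earlier event counts as worse. Table 5 in section 5.1 plans 12-month mortality of 30% in both arms and places all expected benefit in function and days at home. Section 1.2 also says that surgery is unlikely to prolong life.

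**The concern.** The subgroup variable is expected survival at one year, and the first level of the hierarchy is survival to one year. Where mortality is higher, more pairs are settled at a level where no arm effect is planned, and fewer reach the levels where the benefit is planned. The subgroup win ratios can then differ although resection does the same for function and days at home in both subgroups. The difference has the sign that the protocol predicts. A reader could take it as evidence that resection works better in patients expected to live longer, and it could influence which patients are offered the more invasive operation. A better interaction test would not remove this, because it comes from the scale.

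**Working it through.** **Inputs (Table 5).** Mortality 30% in each arm. Function, worst to best: resection 5/20/40/25/10%, fixation 10/25/40/20/5%. Days at home 340 (SD 20) vs 300 (SD 20). Test: "two-sided alpha of 5% tested with the U-statistic described by Bebu and Lachin".

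**The plan's own figures.** The protocol states that "we determined that 300 patients (150 per group) provided over 90% power". Enrolment: 300/0.90 = 333.3, so 334, as stated. Simulating Table 5 (3,000 runs) gives 91% power if mortality is yes/no and both-dead pairs pass down to function and days at home. It gives 79–80% under the section 5.2.2 rule that the earlier death loses. The stated power thus matches the first reading and the analysis text the second, so both are carried below.

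**Pairs with both patients alive.**
- Function win: 0.20×0.10 + 0.40×0.35 + 0.25×0.75 + 0.10×0.95 = 0.4425
- Function loss: 0.25×0.05 + 0.40×0.25 + 0.20×0.65 + 0.05×0.90 = 0.2875
- Tie: 1 − 0.4425 − 0.2875 = 0.27
- Days-at-home win: Φ(40/(20√2)) = 0.921
- Overall win: 0.4425 + 0.27×0.921 = 0.691; loss 0.309

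**Win ratio as a function of mortality.** Let m be 12-month mortality, equal in both arms. The share of pairs reaching function is s = (1−m)², and the other pairs split evenly:

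WR(m) = [(1−s)/2 + 0.691s] / [(1−s)/2 + 0.309s]

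- m = 0.30: s = 0.49, 0.594/0.406 = 1.46
- m = 0.15: s = 0.7225, 0.638/0.362 = 1.76
- m = 0.45: s = 0.3025, 0.558/0.442 = 1.26

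**Comparison of subgroups.** Subgroup mortality and sizes are assumptions: 75 per arm per subgroup, mortality averaging 30%. Effects on function and days at home are identical in both subgroups. The test is a two-sided 5% z-test on the difference of the two log win ratios with the U-statistic variance.

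| Mortality, long/short | Win ratio, long vs short | Hypothesised direction | Rejects |
|---|---|---|---|
| 30/30% | 1.46 vs 1.46 | 50% | about 5% |
| 25/35% | 1.55 vs 1.39 | about 66% | about 7% |
| 20/40% | 1.65 vs 1.32 | 79% | about 12% |
| 15/45% | 1.76 vs 1.26 | 89% | about 24% |
| 10/50% | 1.90 vs 1.21 | 96% | about 36% |

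With unequal mortality, nearly all rejections fall in the hypothesised direction. At 15/45% the longer-expectancy subgroup taken alone is significant in 84% of trials and the shorter one in 21%. Simulation error is one to two percentage points at most: 1.96×√(0.36×0.64/3000) = 1.7 points.

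**Sensitivity, for the 20/40% to 10/50% gaps.**
- Both-dead pairs pass to lower levels: rejection about 7% to 14–16%. The win ratio falls only from 1.80 at 15% mortality to 1.48 at 45%, with its lowest value near 50%.
- Days-at-home difference of 10 days instead of 40: about 7% to 16%.
- No days-at-home effect: about 6% to 9%.
- Benefit on mortality only (assumed hazard ratio 0.8): the pattern reverses, 1.06 at 15% mortality and 1.16 at 45%.

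Section 5.2.2 also mentions local recurrence as a last level. It was not modelled; few pairs would reach it.

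**The case against.** The strongest reply concerns the estimand. Stakeholders ranked death first, so if more patients in a subgroup die within the year, the composite shows less net benefit there, and a lower win ratio answers the question asked. Any effect measure has interactions that depend on its scale. This stands as a reason to keep the subgroup win ratio. It does not make that ratio sufficient. Function is measured at 4 months, so a patient who dies at month 8 can have a 4-month score, yet under section 5.2.2 that score never counts. A lower win ratio cannot show whether surgery did less for function or whether fewer pairs reached function.

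Other limits also stand. Life expectancy is a surgeon's estimate and every entrant needs at least six months, so the real mortality gap may be small. The largest figures need Table 5's very large days-at-home effect and the rule that the earlier death loses. The subgroup analysis is exploratory, and the section names no interaction test; the z-test above is one natural choice. Read literally, stratifying could mean one pooled stratified estimate, which would not assess effect modification at all.

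A reader might infer that the subgroup hypothesis will usually be confirmed even when there is nothing to find. The figures do not support that: 64% to 93% of simulated trials show no significant difference. A reader might also infer that a correctly predicted sign would earn credibility under ICEMAN. The protocol does not set out those criteria, so nothing here rests on them.

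**Conclusion.** The point holds as a weakness of using the win ratio as the only stated scale for effect modification. With the section 5.2.2 rule and Table 5 effects, a mortality difference between life-expectancy subgroups shifts their win ratios apart in the predicted direction with no difference in what surgery does to function or days at home. The shift is modest at a 10-point mortality gap (1.55 vs 1.39, rejection about 7%) and large at a 40-point gap (1.90 vs 1.21, about 36%). Under the milder sensitivity settings, rejection for gaps of 20 to 40 points is about 6% to 16%.

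This rests on assumed subgroup mortality and sizes, and on the benefit lying below mortality, as the protocol itself assumes. For fracture status the problem arises only if mortality differs between impending and realized fractures; the documents give no figure for that, so no bias there is claimed.

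**What to change.** In section 5.2.3, do not rest the conclusion on the subgroup win ratios alone. Pre-specify an arm-by-subgroup term for each component:
- 4-month function: an ordinal or other regression model in all patients with a 4-month score, including those who die later
- days at home: a suitable model, stating how time after death is counted, since otherwise mortality re-enters through this outcome
- mortality: the Cox model already planned among the secondary analyses

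Report the win ratio by subgroup beside these, with the share of pairs settled at each level.

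A win ratio restricted to pairs with both patients alive at 12 months can be supportive only. In a check at 15/45% mortality (64 and 41 survivors per arm) it was 2.24 in both subgroups, pointed either way equally often and rejected in 4.4% of trials. That check assumed equal mortality between arms and deaths unrelated to function, so it could not reveal the selection that comes from conditioning on survival. The restriction also drops 4-month scores of patients who die later.

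Cost: one paragraph and a little programming, with no new data. The downside is a few more exploratory tests with low power.

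### The subgroup analysis stratifies the win ratio to assess effect modification, but no test of a difference between subgroup effects is stated

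*Protocol*

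**What the plan says.** Section 2.2 sets directional hypotheses about the more invasive operation: "patients with a longer life expectancy and those with an impending fracture prior to surgery will have greater treatment benefits". Section 5.2.3 (Subgroup Analyses) repeats them and names the method: "We will stratify our primary model by the subgroup covariate to assess the presence of effect modification". It then adds: "We will assess the credibility of any observed subgroup effects using the Instrument to assess the Credibility of Effect Modification Analyses (ICEMAN) criteria".

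The primary model is defined in section 5.2.2, where "each participant in the clinical trial is compared with every other participant within each stratum in a pairwise manner". Its result is a single ratio: "The Win Ratio is the frequency of a favorable outcome in participants assigned to resection and reconstruction divided by the frequency of a favorable outcome". The denominator refers to the internal fixation arm, and the ratio has one confidence interval and one p-value. Section 5.2.2 does not say what a stratum is.

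Section 4.4 states that "the randomization process will be stratified by: 1) impending or pathologic fracture, and 2) clinical site". Section 1.6.2 gives the reason for the first factor: the treatment effect may differ by fracture status. Life expectancy is not a randomization factor. Section 5.2.1 makes secondary analyses exploratory, without multiplicity adjustment, and section 5.2.3 also presents the subgroup work as exploration.

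**The concern.** Effect modification is a statement about a difference between two effects. A stratified analysis answers another question: what the overall effect is once patients are compared only with others in the same stratum. The protocol assigns the second analysis to the first question.

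The risk is misreading. If the treatment works equally well in both subgroups, the stratified p-value will usually be small. If it helps one subgroup and harms the other, the p-value can be unremarkable. A reader who takes it as evidence on effect modification could conclude the reverse of the truth. The ICEMAN appraisal would also start without a prespecified between-subgroup statistic, and one chosen after the results are seen carries less weight.

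**Working it through.** **Inputs from the protocol (section 5.1 and Table 5).** 150 patients per arm; two-sided alpha 5%; 12-month mortality 30% in both arms; function, worst to best, 5/20/40/25/10% with reconstruction and 10/25/40/20/5% with fixation; days at home 340 (SD 20) and 300 (SD 20); the cited U-statistic variance.

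**Assumptions, not in the protocol.** Independent components; subgroup splits of 50:50 and 70:30; only the three Table 5 components are simulated; where death times are used, they are uniform over the year.

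**The plan's own figure.** With mortality compared as 12-month status and all mortality ties passed down the hierarchy, 10,000 runs give a win ratio (WR) of about 1.57 and 91.4% power, which reproduces the stated figure of over 90%. With death compared by time, the WR is about 1.46 and power 79.7%. Inflation for attrition is 300/0.90 = 333.3, so 334, as stated.

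**Two statistics computed on the same simulated trials.**

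- Stratified WR = Σ(W_s/N_s) / Σ(L_s/N_s), where W_s and L_s are the wins and losses within stratum s and N_s is its size.
- Contrast z = (log WR1 − log WR2) / sqrt(SE1² + SE2²).

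Results with mortality as status, 4,000 runs per row. In the 70:30 rows with unequal effects, the larger subgroup has the Table 5 benefit.

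| True effect in the two subgroups | Split | Stratified WR | Stratified test rejects | Contrast rejects |
|---|---|---|---|---|
| Same (about 1.57 in both) | 50:50 | 1.57 | 91.0% | 4.2% |
| | 70:30 | 1.57 | 90.5% | 5.0% |
| All benefit in one (1.57 and 1.00) | 50:50 | 1.25 | 38.2% | 37.9% |
| | 70:30 | 1.37 | 64.3% | 33.7% |
| Opposite (1.57 and about 0.61) | 50:50 | 0.98 | 4.7% | 93.4% |
| | 70:30 | 1.18 | 24.2% | 89.0% |

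The opposite-effects rows use an invented reconstruction profile in the second subgroup (function 20/30/35/12/3%, days at home 260). They show how the statistics behave and are not a forecast.

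**Check by hand, opposite effects, 50:50.** ln 1.57 = 0.451 and ln 0.61 = −0.494. Their average is −0.02, a WR of 0.98, so pooling cancels the two effects. Their difference is 0.945. With SE 0.279, z = 3.39, and power is Φ(3.39 − 1.96) = Φ(1.43), about 92%, close to the simulated 93%.

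**What the contrast can detect.** Its SE is about 0.27 to 0.31. For 80% power the ratio of win ratios must be exp(2.80 × SE): exp(2.80 × 0.27) = 2.13 and exp(2.80 × 0.31) = 2.38. At SE 0.28, a ratio of 2.0 has power Φ(0.693/0.28 − 1.96) = Φ(0.52), about 70%. If all of the Table 5 benefit lies in one subgroup, power is 38% (50:50) or 34% (70:30). With death compared by time, it is 28% or 25% (2,000 runs).

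**Fracture status.** If the strata in section 5.2.2 are fracture status by site, every primary pair already shares a fracture status. Adding fracture status as a stratifier leaves the set of pairs, and so the result, unchanged. Stratifying by life expectancy would change the pairs but would still return one pooled ratio.

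**The case against.** The strongest reply is that to stratify may here mean running the analysis separately in each level. The sentence gives effect modification as its purpose, and the next one speaks of observed subgroup effects, which requires results by subgroup. On that reading two win ratios with standard errors exist and a contrast can be formed from them. The reading is fair. It does not supply the test, because two separate estimates or p-values do not test their difference.

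A reader might infer that the fracture-status analysis merely repeats the primary one. The protocol does not establish this. It requires the strata of section 5.2.2 to be the randomization strata, which is natural but not stated, and it requires the pooled reading. If the subgroup run were stratified by fracture status alone, without site, the pairs would differ. It never applies to life expectancy.

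It may also be said that the formula of an exploratory interaction test belongs in the statistical analysis plan, which is not at hand and may contain it. That would excuse silence. Here the protocol names a method and gives it a purpose that, in the sense of section 5.2.2, it does not serve. The exploratory status does limit how serious the point is.

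**Conclusion.** The point stands in limited form. On the pooled reading, the stated method does not assess effect modification: it rejects in about 91% of trials when there is none and in 5% to 24% when effects are opposite. On the separate-estimates reading, the needed comparison is not stated. One might conclude that the subgroup hypotheses cannot be answered at all. That goes too far, because the trial data allow a contrast and the analysis plan may add one.

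Even with the right test, power is modest: a ratio of win ratios of about 2.1 to 2.4 is needed for 80% power. These sizes rest on 300 analysed patients, independent components and the assumed subgroup splits, since the protocol gives no subgroup shares. The primary inference is not affected. The sentence should be corrected, but nothing confirmatory depends on it.

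**What to change.** Replace the sentence in section 5.2.3 (Subgroup Analyses) with:

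> *We will estimate the win ratio with 95% CI separately in each subgroup level and test effect modification by the difference in log win ratios, z = (log WR1 − log WR2)/sqrt(SE1² + SE2²), reported as a ratio of win ratios with 95% CI. This result informs the ICEMAN assessment.*

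In section 5.2.2, say which strata the primary analysis uses. In section 5.2.3, say whether they are kept within subgroups; keeping site strata inside a subgroup may leave few pairs. Add that the analysis is exploratory with low power, giving the detectable ratio and its assumptions.

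The cost is a few sentences in the protocol or the analysis plan, with no new data and no change to sample size. It should be done before unblinded results are seen.

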5.2.4 Health Economic Analysis

An economic evaluation of this trial will be conducted to compare the one-year costs and outcomes between the two treatment allocations. QALYs will be utilized as the primary outcome, as is recommended in many countries (e.g., Canada, the United Kingdom and the United States)²⁷⁻²⁹. Life years (LYs) will be used as a secondary outcome.

For the base case analysis, Canadian unit costs will be applied to the economic data collected as part of the trial to estimate the direct (e.g., hospitalizations, surgeries) and indirect costs (e.g., productivity losses) associated with the two treatment allocations. QALYs will be derived using the health utility scores from the PROMIS-PROPr questionnaires collected in the trial using an area under the curve. The base case analysis will use the Canadian algorithm to derive the PROMIS-PROPr health utility scores³⁰. Multiple cost-effectiveness acceptability curves (CEACs) presenting the probability of each of the treatment allocations to be cost-effective at several willingness-to-pay thresholds (e.g., \$50,000 or \$100,000 per QALY gained) will be used to summarize uncertainty. Costs and outcomes will be discounted at 1.5% as per the recommendations of the current Canadian guidelines, and results will be presented from both a payer (e.g., Ministry of Health) and a societal perspective²⁷. Scenario analyses will be conducted to explore the impact of varying key assumptions on the results (e.g., using unit costs from the United States, discount rate of 3%). The analysis will be conducted and reported according to best practices for economic evaluations of healthcare technologies (e.g., how to deal with missing or censored data)^{31,32}.

5.2.5 Sensitivity Analyses

Assessment of the sensitivity or robustness of the findings to the key assumptions is essential in clinical trials. The following sensitivity analyses will be performed:

- 1) Baseline Prognostic Imbalance Analysis: This analysis will assume a baseline prognostic imbalance between the treatment groups. Adjusted analyses, employing Cox regression models, will be utilized to examine and control for the possible influence of patient factors that might be associated with the elements of the hierachal composite outcome.
- 2) “As-Treated” Analysis: This sensitivity analysis will account for crossovers in the surgical intervention. The actual surgical intervention will be the independent variable.

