3.2 Outcome Measures

3.2.1 Primary Outcome: Hierarchical Composite Outcome

The primary outcome for the PERFORM trial will be a patient-centered hierarchical composite endpoint, including the four constructs we identified in our stakeholder and patient engagement framework: 1) Mortality as assessed at 12 months, 2) Physical function as assessed at 4 months using the Patient-Reported Outcomes Measurement Information System (PROMIS®) Global Physical Function score, and 3) Number of days at home as determined at 12 months. The data (**Table 2**) below has been extrapolated from the literature and will be hierarchically assessed in the order listed below. The hierarchical order was determined by discrete choice experiment responses from surgeons, caregivers and patient partners (n=86) that allowed for prioritization of the outcomes within the hierarchy.

Table 2. Expected Proportion of Outcomes in the Sample (Stratified by Treatment Arm)

Level	Outcome	Expected Outcomes		
		Overall	Internal Fixation	Resection and Reconstruction
1	Mortality at 12 months	30%	30%	30%
2	PROMIS Global Physical Function (patient-reported outcome measure) * at 4 months	3.5	4.0	3.0
3	Days at Home ** at 12 months	320	300	340

* Higher values = better function, minimal clinically important difference is 0.5. 'To what extent are you able to carry out your everyday physical activities such as walking, climbing stairs, carrying groceries or moving a chair?' (Range 5: completely to, 1: not at all).

** Days with no interaction with the healthcare system, patient diary reported

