4.6 Data Collection and Participant Follow-Up

At baseline, we will collect pre-operative demographic and cancer-related data from various sources, including the participant or proxy, the participant's medical chart, and/or the participant's treating surgeon. The data will include details such as age, sex and gender, co-morbidities, life-expectancy based on surgeon estimate and pre-surgical functional status, and anatomic characteristics of the femoral metastatic lesion. Participants will also pre-operatively complete the PROM questionnaires. We will document surgical details, peri-operative care, and in-hospital data, including the timing of surgery and any co-interventions used that may mediate treatment effects (such as post-operative mobilization and therapy), as well as any serious adverse events (SAEs) that occurred during hospitalization. After discharge, participants will be followed for one year, during which they will be assessed by their treating surgeon at two and six weeks; four, six and nine months; and one-year post-surgery. At each visit, we will document physical therapy, ability to ambulate, re-operations, hospitalizations, and SAEs. PROM data will be collected at all visits; however, the burden is low due to the short nature of the questionnaire. The utility score from the PROPr: PROMIS®-Preference Scoring System will be collected at baseline and 6 and 12 months. Trial data will be securely stored in the trial database accessible only to authorized personnel. See **Table 4** below:

Table 4. Study Flow

CATEGORY	STEPS		DATA COLLECTED
Recruitment	Identification of Patients		
	Assessment of Patient Eligibility		Screening Data
	Informed Consent		Informed Consent Form
Pre-Operative (Baseline)	Pre-Operative (Baseline)		Demographics Cancer-related data PROMIS®-PROPr questionnaire PROMIS® Physical Function
	RANDOMIZATION 		
Follow Up Visits	Internal Fixation	Resection and Reconstruction	
	Peri-Operative	Peri-Operative	Surgical details Peri-operative care Serious Adverse Events (SAEs)
	2 Week	2 Week	Follow-Up Data Package: X-rays; PROMIS® Physical Function questionnaire; Demographics, health-related questions, Mortality Status; Patient-reported days at home; Recurrence of cancer; SAEs
	6 Week	6 Week	Follow-Up Data Package: X-rays; PROMIS® Physical Function questionnaire; Demographics, health-related questions, Mortality Status; Patient-reported days at home; Recurrence of cancer; SAEs

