5.2.3 Secondary Outcomes Analyses

We will analyze all-cause mortality with a Cox proportional hazards model, re-operation for disease relapse and other indications with frailty models to account for recurrence, and patient-reported outcomes using linear regression models.

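### The baseline-imbalance sensitivity analysis names only Cox regression, which fits mortality alone among the composite's three defined components and leaves the win ratio without a covariate-adjusted version

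*Protocol*

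**What the plan says.** Section 5.2.5 lists two sensitivity analyses. The first is written for an imbalance: "This analysis will assume a baseline prognostic imbalance between the treatment groups". Its method is "Adjusted analyses, employing Cox regression models, will be utilized to examine and control for the possible influence of patient factors", and the factors meant are those linked to the components of the composite, in the plural. No other model is named there.

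Section 3.2.1 defines three components in order: death by 12 months, a five-level physical function item at 4 months, and "Number of days at home as determined at 12 months". Section 5.1 powers the trial on the same three. Section 5.2.2 analyses them with a win ratio, comparing participants pairwise within strata that it does not define. It also mentions local recurrence as a last level, which sections 3.2.1 and 5.1 do not contain.

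Elsewhere the protocol matches model to outcome: section 5.2.3 (Secondary Outcomes Analyses) uses Cox for mortality and analyses "patient-reported outcomes using linear regression models". Under section 4.4, "the randomization process will be stratified by: 1) impending or pathologic fracture, and 2) clinical site".

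**The concern.** Cox regression is a model for time to an event. A five-level score at a fixed visit and a count of days are not times to an event, and a Cox model does not adjust a win ratio. The one adjusted analysis that the protocol names therefore reaches one component of three, and it is the one in which no difference is planned.

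Suppose the trial ends with a favourable win ratio and the arms differ visibly in baseline function. Readers will ask whether the result survives adjustment. As written, the plan gives them an adjusted hazard ratio for death and no adjusted counterpart to the primary estimate. A method for that would then be chosen after the data are known.

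**Working it through.** **Inputs.** From section 5.1 and Table 5: 150 evaluable per arm; deaths 30% and 30%; function, worst to best, 5/20/40/25/10% (resection) and 10/25/40/20/5% (fixation); days at home 340 (SD 20) and 300 (SD 20). The correlations, the size of the imbalance and the exponential death times used below are assumptions; the protocol does not give them.

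**The plan's own figures.** 300/(1 − 0.10) = 333.3, so 334 enrolled, as stated. In 3,000 simulated trials with the large-sample win-ratio variance, power is 91% if death is compared as yes/no and ties pass down. This agrees with the stated power of over 90%. With deaths compared by time, as section 5.2.2 describes, power is 78–79%. That is a separate matter, so both versions are carried here.

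**Where the planned effect lies (Table 5).**
- Function: win = 0.20×0.10 + 0.40×0.35 + 0.25×0.75 + 0.10×0.95 = 0.4425; tie = 0.27; loss = 0.2875; net 0.155.
- Days: win = Φ(40/(20√2)) = Φ(1.414) = 0.921; net = 2×0.921 − 1 = 0.843 (from unrounded values).
- Pairs undecided by death: 0.7² + 0.3² = 0.58 (yes/no), or 0.7² = 0.49 (by time).
- Net benefit, yes/no: function 0.58×0.155 = 0.090; days 0.58×0.27×0.843 = 0.132; mortality 0. By time: 0.076, 0.111 and 0.
- Shares in either version: function 40.5%, days 59.5%, mortality 0%.
- Win ratio: 1.570 (yes/no) or 1.461 (by time).

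**What the Cox model would give in the planned case.** About 0.30×300 = 90 deaths; SE of the log hazard ratio = 2/√90 = 0.211; 95% CI around a ratio of 1 is exp(±1.96×0.211) = 0.66 to 1.51.

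**How often imbalance arises by chance.** SE of a standardized baseline difference = √(2/150) = 0.1155. In favour of resection: P(≥0.2 SD) = 1 − Φ(1.732) = 4.2%; P(≥0.3 SD) = 1 − Φ(2.598) = 0.47%. Counting both directions doubles these to 8.3% and 0.9%.

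**What such an imbalance does.** Simulation, 1,500 trials per setting, no treatment effect, one baseline factor 0.2–0.3 SD better under resection, correlation 0.3–0.7 with function and days:
- Factor unrelated to death: win ratio 1.04–1.16; false favourable results 4–19% against a nominal 2.5%; mortality hazard ratio 0.99–1.01 both before and after adjustment, so Cox shows nothing.
- Factor that also predicts death (hazard ratio 0.74 per SD): win ratio 1.07–1.22; false favourable results 6–27%. Adjustment moves the mortality hazard ratio from 0.90–0.95 to 0.99–1.01, so Cox does respond, but the win ratio stays unadjusted.
- Weighting the win ratio by inverse probabilities from the baseline factor returns it to 0.995–1.005 in both cases. Treating those weights as fixed made the test conservative (false favourable 0.9–2.5%).

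**The case against.** **The stakes are small.** This stands. It is one supporting analysis; the imbalances above are uncommon; the upper ends of the false favourable ranges belong to the 0.3 SD extreme, about 1 trial in 200; and a drift to 1.04–1.16 is small beside a planned 1.46–1.57. A reader might infer that the primary result is biased or its alpha inflated. The documents do not support that: averaged over randomizations the alpha is intact.

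**Cox is not useless here.** This also stands. A reader might note that the adjusted Cox test is significant in about 5% of simulated trials whatever the cause of a favourable win ratio, and conclude that it cannot separate a real effect from an imbalance. That is circular: the mortality effect was fixed at zero, so a 5% test must reject about that often. A sensitivity analysis is read by comparing estimates before and after adjustment, and on that reading Cox detects a factor that predicts death.

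**The 41%/59% split is not the plan's only picture.** Correct. Table 2 gives mean function as 4.0 for fixation and 3.0 for resection with higher meaning better, the reverse of Table 5 (means 2.85 and 3.15). That needs its own reconciliation. Equal mortality is common to both tables, and the point rests on that.

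**Strata already adjust.** Only in part. Fracture status and site do not cover baseline function or life expectancy, and the subgroup analysis stratifies to look for effect modification.

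**Cox could serve recurrence.** Recurrence is a level only in section 5.2.2. Under Table 5 with complete data fewer than 0.1% of pairs would reach it; with missing function or diary data the share could be larger. Function and days would still be uncovered.

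**The estimator belongs in the SAP.** Details do. But the protocol is not silent: it names a model that does not fit two of the three components it is meant to cover.

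**Conclusion.** The point holds as a misfit between a stated method and its stated purpose, of minor to moderate severity. The named analysis covers mortality only and gives no covariate-adjusted version of the win ratio. It would miss an imbalance acting only through function or days at home, where Table 5 places the whole planned benefit.

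The mismatch itself follows from the text and needs no assumption. The sizes do: the shares depend on Table 5, and the drift to 1.04–1.16 depends on the assumed imbalance of 0.2–0.3 SD and correlations of 0.3–0.7.

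**What to change.** Replace the Cox sentence in section 5.2.5, for example with:

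> The primary win ratio will be re-estimated with inverse-probability weights built from baseline PROMIS physical function and surgeon-estimated life expectancy (and fracture status, if it is not a stratum of the primary analysis). The strata of the primary analysis are kept, and the confidence interval comes from a bootstrap that re-estimates the weights. As supporting analyses, mortality will be reported from an adjusted Cox model, and 4-month function and days at home from adjusted models suited to each outcome type, with the handling of participants who died stated for each.

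Weighting is one valid choice among several. An advantage over fine covariate strata is that it leaves the estimate alone when there is nothing to correct. With the planned effect and no imbalance, quintile strata moved the win ratio from 1.57–1.59 to 1.61–1.88 (yes/no) or from 1.46–1.47 to 1.50–1.68 (by time). With the planned effect and a 0.2 SD imbalance, weighting brought 1.63–1.74 back to 1.57–1.59, and 1.51–1.58 back to 1.46–1.47. The remaining detail can go to the SAP. Handling of deaths must not be left open, because 30% are expected to die by 12 months.

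The cost is a short text change and slightly more programming. The data are already collected under section 4.6: "Participants will also pre-operatively complete the PROM questionnaires", and the baseline record includes "life-expectancy based on surgeon estimate and pre-surgical functional status". Weighting cost no visible power in simulation (91–93% unweighted and 92–94% weighted for yes/no; 78–80% and 79–80% by time). The primary test, alpha and 334 enrolled stay as they are.
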